## 5. Selection of Patients

Eligibility is determined at the time of screening. Approval of protocol deviations related to recruitment and enrollment criteria, also known as protocol waivers or exemptions, are not permitted.

The target population for this study is patients with severe COVID-19, per FDA guideline.

### 5.1. Inclusion Criteria

*Patients can be enrolled into this study if all of the following criteria are met at screening visit:*

1. Hospitalized patient with clinical diagnosis of SARS-CoV-2 virus infection per World Health Organization criteria including positive nucleic acid test of any specimen (e.g., respiratory, blood, or other bodily fluid) within 2 weeks prior to screening.
2. Symptoms suggestive of severe systemic illness with COVID-19, which could include any of the following symptoms: fever, cough, sore throat, malaise, headache, muscle pain, gastrointestinal symptoms, or shortness of breath at rest, or respiratory distress.
3. Clinical signs indicative of severe systemic illness with COVID-19, which could include any of the following clinical signs: respiratory rate  $\geq 30$  per minutes, heart rate  $\geq 125$  per minute,  $\text{SpO}_2 \leq 93\%$  on room air,  $\text{PaO}_2/\text{FiO}_2$  ratio  $< 300$  mmHg, or lung infiltration  $>50\%$  on chest X-ray imaging.
4. Patients with plasma CRP level  $>50$  mg/L or 4x upper limit of normal range at screening.
5. Men or women  $\geq 18$  but  $\leq 80$  years of age at the time of signing the informed consent form.
6. Use of home oxygen is allowed
7. Patient is able to understand the purpose and risks of the study and provide signed and dated informed consent or have a legal representative provide consent and authorization to use protected health information (in accordance with national and local patient privacy regulations).
8. Patient is able to swallow tablets or receive delivery of oral suspension via a nasogastric tube.
9. Patient agrees not to participate in another interventional study after signing the informed consent form and until the end of study (EoS) visit has been completed.

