### ***Vital Sign Measurements***

Vital sign data (SBP and DBP, heart rate, respiratory rate, and oral temperature) will be summarized by presenting summary statistics for change from baseline values. The incidence rates of clinically significant vital sign abnormalities will be summarized.

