Informed consent	X									
Medical history	X									
Demographics	X									
Physical examinations	X ⁴								X	
Vital signs ⁵	X	X	X	X	X	X	X	X		X

12-lead ECG	X	X ⁶		X		X		X	X
Blood samples for routine lab tests including CRP and ferritin ⁷	X	X	X	X	X	X	X	X	X
Blood samples for coagulopathy and cardiac panels ⁸		X	X	X		X		X	X
Urine sample for urinalysis	X	X	X	X		X		X	X
Serum serology and pregnancy tests for screening	X								
Inclusion and exclusion	X								
Randomization		X							
Treatment		X	X	X	X	X	X	X	
Oxygen use and saturation (pulse oximetry)	X	X	X	X	X	X	X	X	X
PaO ₂ /FiO ₂ ratio	X	X		X				X	
WHO ordinal scale		X		X				X ¹³	X
Blood sample for cytokine/chemokine panels and CV biomarkers ⁹		X		X				X	
Blood sample for PK analysis and pRIP1/pMLKL assay ¹⁰		X		X				X	
Urine sample for NGAL and KM-1 assay ¹¹		X		X				X	
AE and ConMed	X	X	X	X	X	X	X	X	X

1. Enrollment and Baseline. Screening and Baseline visits can be combined. ECG, laboratory test and other test results taken within 24 hours prior to consent will be used as Baselines.
2. End of Treatment (EOT) or early discharge.
3. End of the study (EOS) or early discontinuation.
4. For enrolled patients, physical examination obtained at screening will be the Baseline. Weight and height will be measured at screening.
5. Vital signs will be taken before the 1st dose on Day 1 as Baseline, and within 3 hours before the 2nd dose on other days.
6. Three ECGs with 1-3 min interval before the 1st dose on Day 1 only, and the means of the 3 ECGs will be used as Baselines. ECGs will be done within 3 hours before the 2nd dose on other days. Local ECG machine will be used in this study.
7. Routine laboratory tests before the 2nd dose will be done daily at local labs. CRP and ferritin tests will be done on Days 1, 3, 7, 10 and 14.
8. Coagulopathy panel including D-dimer, fibrinogen, PT, PTT and INR, and cardiac function panel including NT-proBNP (or BNP) and high-sensitivity cardiac troponin will be done on Days 1, 3, 7, 10 and 14 at local labs with samples collected before the 2nd dose.
9. One blood sample collected before the 1st dose on Day 1 and before the 2nd dose on Days 7 and 14 for cytokine/chemokine panels and CV biomarker assays to be conducted at a central lab

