11.4 Vital Signs

Vital sign data will be summarized by presenting summary statistics for observed and change from Baseline values, by visit and treatment group. Temperature will be collected in °C (Celsius) or °F (Fahrenheit) in eCRF, all values will be converted to °C for analysis.

The °F values will be converted using the formula given below.

$$^{\circ}\text{C} = (^{\circ}\text{F} - 32) * /9$$

Descriptive statistics for the following vital signs will be presented:

- Systolic blood pressure (mmHg)
- Diastolic blood pressure (mmHg)
- Heart rate (beats/min)
- Respiration rate (breaths/min)
- Body temperature (°C)

The incidence rates of vital sign abnormalities (refer to [Appendix 4: Criteria for Abnormal Values for Vital Signs](#)) will be summarized by treatment group. A second summary table will also be produced, summarizing the incidence rates of vital sign abnormalities by treatment group and visit.

The incidence rates of clinically significant vital signs will be summarized by treatment group, as well as by treatment group and visit.

A data listing of vital signs will also be created.

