Appendix 4: Criteria for Abnormal Values for Vital Signs

Vital Signs	Criterion Value
Heart Rate	< 54 beats/min > 120 beats/min
Respiration Rate	< 10 breaths/min > 17 breaths/min
Systolic Blood Pressure	< 90 mmHg > 140 mmHg
Diastolic Blood Pressure	< 60 mmHg > 90 mmHg
Body Temperature	< 35 °C > 38 °C

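### The vital-sign abnormality tables in SAP 11.4 have no baseline condition, so illness present at admission can be counted as on-study abnormality

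*Protocol*

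**What the plan says.** - **Limits.** SAP Appendix 4 sets fixed limits. The respiratory-rate row is "< 10 breaths/min > 17 breaths/min" and the heart-rate row is "< 54 beats/min > 120 beats/min".
- **Use of the limits.** SAP 11.4 begins "The incidence rates of vital sign abnormalities (refer to" Appendix 4) and reports them by treatment group (Table 14.3.7.2). It adds a second table "summarizing the incidence rates of vital sign abnormalities by treatment group and visit" (Table 14.3.7.3). Neither sentence sets a condition on the baseline value.
- **Entry signs.** Protocol 5.1, criterion 3, lists "Clinical signs indicative of severe systemic illness with COVID-19, which could include any of the following clinical signs: respiratory rate" of at least 30, heart rate of at least 125, SpO2 of 93% or less on room air, PaO2/FiO2 below 300 mmHg, or lung infiltration above 50%. Any one is enough.
- **Baseline data.** The fifth footnote to SAP Table 5.2 reads: "Vital signs will be taken before the 1st dose on Day 1 as Baseline, and within 3 hours before the 2nd dose on other days". The value needed for a baseline comparison is therefore collected.
- **Other vital-sign displays.** SAP 11.4 also plans observed values and change from baseline by visit, and counts of clinically significant vital signs. The latter answer Protocol 10.3.2: "The incidence rates of clinically significant vital sign abnormalities will be summarized".
- **Elsewhere in the plan.** Protocol 10.3.2 defines a TEAE as an event that starts or worsens after the first dose. SAP 11.3 plans shift tables from baseline to the most extreme post-baseline value for laboratory data. SAP Appendix 5 lists baseline shift tables for the coagulopathy and cardiac panels. Its five vital-sign tables (14.3.7.1 to 14.3.7.5) include none.

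**The concern.** A patient who enters on respiratory rate or heart rate is beyond the Appendix 4 flag at screening. If the sign persists to a scheduled reading after dosing, SAP 11.4 counts it as an abnormality under study treatment. The same rule counts a patient whose value was normal on Day 1 and rose on drug, and the table cannot tell the two apart.

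Table 14.3.7.2 also accumulates over daily readings. A low limit such as 17 breaths/min can push its respiratory row towards a ceiling in both arms, where a real difference is hard to see. Vital signs are a named safety assessment under the primary objective, and the plan refers to baseline in its other main safety displays, so this one is out of line with them.

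**Working it through.** The plan states no expected abnormality rate, so there is no figure to reproduce.

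**1. Limits against entry signs.** Respiratory rate: 30 − 17 = 13 breaths/min. Heart rate: 125 − 120 = 5 beats/min. Entry on either sign means a screening value at least that far beyond the flag. By contrast, the lower blood-pressure flags (90 systolic, 60 diastolic) match exclusion criterion 2, so values below them are excluded at screening.

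**2. Number of readings.** Days 2 to 14 give 13, and Day 28 makes 14 scheduled post-baseline readings at most. Early discharge gives fewer.

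**3. How an ever-abnormal row accumulates.** For independent readings, P(ever flagged) = 1 − (1 − p)^k, where p is the per-reading probability (an assumption) and k the number of readings.

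| p | k = 6 | k = 14 |
|---|---|---|
| 0.02 | 11% | 25% |
| 0.05 | 27% | 51% |
| 0.10 | 47% | 77% |
| 0.20 | 74% | 96% |
| 0.30 | 88% | 99% |

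Reaching 95% needs p = 1 − 0.05^(1/k), which is 0.19 for k = 14 and 0.39 for k = 6. Within-patient correlation lowers the row. A beta-binomial model with correlation 0.5 and k = 14 gives 28%, 65% and 85% at mean p of 0.1, 0.3 and 0.5. The row can therefore be low or near its ceiling, depending on a p that the documents do not give.

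**4. Respiratory rate by simulation.** Assumptions: normal values rounded to integers, within-patient correlation 0.5, a fall of 0.3/min per day and seven post-baseline readings. Share of patients ever above 17:

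- Day 1 mean 16, SD 3: about 54%
- Day 1 mean 20, SD 3-4: about 94-96%
- Day 1 mean 24, SD 3-4: nearly 100%

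**5. Visibility of a drug effect.** The same model with mean 20 and SD 4, without and with a drug-induced rise of 4/min:

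| Display | No effect | +4/min |
|---|---|---|
| Ever above 17 (Table 14.3.7.2) | 94% | 99.7% |
| Above 17 at Day 7 (Table 14.3.7.3) | 57% | 88% |
| Ever above 17 and at least 4 above Day 1 | 39% | 83% |
| Ever at or above 30 | 2-3% | 20-23% |

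No test is specified for these tables, so exact Fisher power at 30 per arm (two-sided 0.05) serves only as a yardstick:

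- 95% against 100%: 0.3%
- Day 7 row: about 71%
- Baseline-referenced row: about 92%
- At-or-above-30 row: about 47%

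Against 30/30 in one arm, the other must have 24/30 or fewer to reach significance (24/30, p = 0.024; 25/30, p = 0.052).

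The planned change from baseline would also show this effect. With an SD of change of about 4, the standard error is 4 × √(2/30) = 1.03, and 4/1.03 is about 3.9 standard errors.

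**6. Loose and strict baseline rules.** In the no-effect case, counting a value above 17 that is worse than Day 1 by any amount still flags about 71% of patients. A margin is needed.

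**The case against.** The strongest reply has four parts.

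- **Entry signs are optional.** Respiratory rate and heart rate are two of five alternatives. A patient can enter on oxygenation or imaging with both values inside the limits, and exclusion criterion 1 removes respiratory failure and ventilated patients. This stands. A reader might infer that the table will be near 100% in both arms. No document says so, and step 4 shows that it depends on the assumed mean. For heart rate no rate has been calculated.
- **Screening is not Day 1.** Criterion 3 applies at screening, up to seven days before dosing, and SAP 8.5 limits tabulated post-baseline values to scheduled ones. An entry sign reaches the count only if it persists or recurs. This stands too, but it does not remove persisting illness from the count.
- **Other displays would show harm.** A reader might also infer that the plan cannot show respiratory harm. It can. In step 5 the by-visit table and the change from baseline both separate the arms. Clinically significant vital-sign abnormalities are also AEs under Protocol Appendix 4, and respiratory failure, the WHO scale, PaO2/FiO2 and mortality are analysed. What remains is that the by-visit table has no baseline condition either, that means can dilute a rise in a few patients, and that SAP 11.4 gives no objective criterion for clinical significance.
- **The table is secondary.** The primary measure is the proportion with any TEAE, and the listed secondary safety measures do not name vital signs. This stands and limits the importance of the point.

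**Conclusion.** The gap is in the text and needs no assumption: Tables 14.3.7.2 and 14.3.7.3 count fixed-limit flags with no baseline condition, and no vital-sign shift table is planned. Table 14.3.7.2 can therefore report admission illness as on-study abnormality.

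That its respiratory row may approach a ceiling is a conditional statement. It rests on an assumed respiratory-rate distribution, correlation and number of readings, and ranges from about 54% to nearly 100% as the assumed mean goes from 16 to 24. For heart rate, the documents support only that admission tachycardia and on-drug events are mixed.

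This is a weakness in one secondary safety display, softened by the other planned summaries. The primary TEAE endpoint is not affected.

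**What to change.** In SAP 11.4, count an Appendix 4 abnormality in Tables 14.3.7.2 and 14.3.7.3 only if it is post-baseline and meets one of two conditions: the Day 1 pre-dose value did not meet the criterion, or the post-baseline value is worse than baseline by a margin fixed for each vital sign before unblinding. The 4/min used above is for illustration only. Add a shift table from baseline to the worst post-baseline value, as SAP 11.3 does for laboratory data. Keep the present absolute count as a supplementary display.

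Do not replace the reporting flags with the entry-sign values of 30 and 125. Patients can be at those values on entry, and in step 5 the cut-off of 30 separates the arms less well than a baseline-referenced count.

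The cost is SAP wording and table programming, with no new data. Counts will be lower than under the current rule.

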### 5.2. Exclusion Criteria

*Patients should be excluded from this study if any of the following criteria is met at screening visit:*

1. Patient requires endotracheal intubation and mechanical ventilation, oxygen delivered by high-flow nasal cannula (heated, humidified, oxygen delivered via reinforced nasal cannula at flow

rates >20 L/min with fraction of delivered oxygen  $\geq 0.5$ . However, periodically delivered at flow rates >20 L/min with fraction of delivered oxygen  $\geq 0.5$  is allowed), noninvasive positive pressure ventilation, extracorporeal membrane oxygenation (ECMO), or clinical diagnosis of respiratory failure.

2. Patient with shock defined by systolic blood pressure < 90 mm Hg, or diastolic blood pressure < 60 mm Hg or requiring vasopressor.
3. Patient with multi-organ dysfunction or failure.
4. Patient is unlikely to survive beyond 2 days at the discretion of Investigator.
5. Patient has used chronic systemic corticosteroids (for example, >32 mg/day methylprednisolone or equivalent) within 2 weeks prior to screening. However, dexamethasone at a stable dose  $\leq 6$  mg/day or equivalent (such as 31.25 mg of Solu-Medrol) is allowed. One dose of dexamethasone at >6 mg but  $\leq 12$  mg or equivalent is allowed, provided baseline CRP level is measured 24 hours after the dexamethasone dosing at >6 mg but  $\leq 12$  mg.
6. Patient with moderate to severe hepatic impairment by Child-Pugh scoring system.
7. Patients with severe kidney injury requiring dialysis.
8. Patient with any of the following abnormal laboratory values: absolute neutrophil count (ANC) < 2,000 per mm^3, or platelets count <50,000 per mm^3, or alanine aminotransferase (ALT) or aspartate aminotransferase (AST) > 5 x upper limit of normal (ULN) detected within 24 hours at screening (per local lab).
9. Patient has uncontrolled or untreated symptomatic arrhythmias, myocardial infarction or congestive heart failure within the 6 weeks prior to screening.
10. Patient has received immunosuppressant or immunomodulatory drugs within 1 month prior to screening, including anti-cytokine therapies targeting TNF- $\alpha$ , IL-1, IL-6, interferon-beta, or Bruton Tyrosine Kinase (BTK) within 30 days prior to screening. However, remdesivir, convalescent plasma therapy or hydroxychloroquine/chloroquine is allowed in this study.
11. Patient with a code status of do-not-resuscitate (DNR) or cardiopulmonary resuscitate (CPR) Select.
12. Patient with positive results for human immunodeficiency virus (HIV) or hepatitis B or C test.
13. Patient has known active tuberculosis (TB), history of uncontrolled TB, sepsis induced by systemic bacterial or fungal infections within 4 weeks prior to screening.
14. Patient is taking any medication that is mainly metabolized by CYP450 2C19 (a list of commonly used medications that are mainly metabolized by CYP450 2C19 can be found in

[Appendix 6](#)). The investigator could provide an alternative medication that is not mainly metabolized by CYP450 2C19.

15. Female patient who is pregnant or lactating or has a positive serum pregnancy test within 72 hours prior to screening and/or randomization, has been pregnant within 6 months before screening or breastfeeding within 3 months before screening or who is planning to become pregnant within the total study period. Woman of Childbearing Potential (WOCBP) must agree to use a highly effective method of contraception consistently and correctly as described in [Appendix 5](#).
16. Patient has a known or suspected hypersensitivity to SIR1-365 or any components of SIR1-365 tablets.
17. Patient has received any investigational drug within 30 days or 5 half-lives, whichever is longer, prior to screening.
18. Patient has any other condition, which makes the patient unsuitable for study participation.

### **5.3. Lifestyle Restrictions**

No restrictions are required.

### **5.4. Screen Failures**

Screen failures are defined as patients who consent to participate in the clinical study but are not subsequently randomized. A minimal set of screen failure information is required to ensure transparent reporting of screen failure patients to meet the Consolidated Standards of Reporting Trials (CONSORT) publishing requirements and to respond to queries from regulatory authorities. Minimal information includes demography, screen failure details, eligibility criteria, and any SAEs. Data for screening failures will be included in the study database.

Individuals who do not meet the criteria for participation in this study (screening failures) may not be rescreened.

## **6. Treatments**

Study treatments include SIR1-365 100-mg tablets and matching placebo tablets.

### 6.1. Treatments Administered

Study Drug Name:	SIR1-365	Placebo
Dosage formulation:	Tablets	Matching tablets
Unit dose strength/Dosage level:	100 mg tablets	NA
Route of Administration	Oral/gastric tube	Oral/gastric tube
Dosing Instructions:	Take 1 tablet three times daily	

Food and water will be allowed as needed.

The first dose of study treatment will be administered in the hospital on Day 1 after all eligibility criteria are met and randomization procedures are completed. The time of first dose establishes time zero for subsequent doses. The exact time of study treatment administration as well as the dosage (number of tablets taken) will be recorded for all doses given while in the hospital.

If hospitalized, patients are to take study treatment according to the dosing schedule (once every 8 hours  $\pm$  1 hour from Day 1 up to Day 14). If any dose of study treatment is missed, defined as no medication intake 1 hour after the scheduled dosing time, the event should be recorded in electronic Case Report Form (eCRF) and the patient should resume dosing at the next scheduled dosing time.

If the disease worsens, the patients may require mechanical ventilation and be unable to swallow study medication. In such cases, the medication will be given as an oral suspension via nasogastric tube. The suspension will be prepared immediately before dosing by dispersing one 100-mg tablet of SRI1-365 in a container with about 20 mL of water and stirring the mixture approximately 3-5 times in about 5 minutes. The oral suspension will be administered within 1-2 minutes after the preparation. The container will then be rinsed twice with about 20 ml of water each, which will be administered to the patient as well. The details for the preparation and administration of oral disintegrated suspension will be included in Pharmacy Manual.

### 6.2. Method of Treatment Assignment

All patients will be centrally randomized using an interactive response technology (IRT). Before the trial is initiated, the login information and directions for using the system will be provided to each site.

### 6.3. Blinding and Unblinding

This is a double-blinded clinical trial. The placebo tablets will match the appearance of SIR1-365 tablets, and each patient will take one tablet, TID.

If a patient becomes seriously ill during the study, the blind will be broken for that patient only if knowledge of the administered study treatment will affect treatment options available to the patient. As soon as possible, the Investigator should first contact the medical monitor to discuss the medical

emergency and the reason for revealing the actual treatment received by that patient. The treatment assignment will be unblinded through the interactive response technology.

If the blind is broken, the date, time, staff involved, and reason must be recorded in the eCRF and any associated reports.

If a patient is unblinded for any reason, the study treatment will be discontinued. The patient will be followed through Day 28 or until early termination from the study.

During the study, unblinded safety, biomarker and clinical efficacy data will be reviewed by an IDMC.

#### **6.4. Dose Modification**

Dose modification is not allowed in this study. At any time, the IDMC may recommend treatment discontinuation if there is a clinically significant safety signal.

#### **6.5. Preparation/Handling/Storage/Accountability**

Only patients enrolled in the study may receive study treatment and only authorized site staff may supply or administer study treatment.

Instructions for suspension preparation and administration will be provided in the Pharmacy Manual.

All study treatments must be stored in a secure, environmentally controlled, and monitored (manual or automated) area in accordance with the labelled storage conditions (controlled room temperature (15-25 °C) with access limited to the Investigator and authorized site staff.

The Investigator is responsible for study treatment accountability, reconciliation, and record maintenance (i.e., receipt, reconciliation, and final disposition records).

At the completion of the study, to satisfy regulatory requirements regarding drug accountability, all study treatment will be reconciled and retained or destroyed according to applicable regulations.

Further guidance and information for preparation, handling, storage and disposition of unused study drugs can be found in the Pharmacy Manual.

#### **6.6. Treatment Compliance**

The Investigator and study personnel should promote compliance by dispensing the study treatment as planned and record the dosing information in the eCRF. The investigational site staff will perform pill counts after dosing or at early termination if a patient discontinues early from the treatment phase; and record the information in the eCRF. Reasons for departure from the expected dosing regimen must also be recorded.

